## **1-Introduction**

Cancer is one of the most pressing global health concerns. It is stated that there will be four million new breast cancer cases in 2030. World Health Organization (1). Anticipate that cancer numbers will increase significantly, especially in low- and middle-income countries(2). Beyond the physical and financial burdens, cancer is now widely recognized for its profound psychological toll. Emotional distress, such as depression, anxiety, insomnia, and anger, has been identified as a 'silent comorbidity' that can impact treatment adherence, recovery outcomes, and overall quality of cancer patients.

Breast cancer is the most commonly diagnosed cancer among women globally including the Middle East and Iraq. According to the Iraqi Ministry of Health (3). More than 5,000 new breast cancer cases are diagnosed annually, representing over 21% of total new cancer diagnoses in the country(2,3). Unfortunately, due to poor access to screening programs, and limited public awareness, most patients are diagnosed at advanced stages, particularly in underserved regions such as Al-Anbar (4). These patients are at greater risk of experiencing severe psychological consequences due to uncertain prognosis, aggressive treatment protocols, and social isolation (5)

Previous research in Al-Anbar has focused on breast cancer patients (4) Largely focused on pharmacological and economic variables, without exploring behavioral and emotional factors such as sleep quality, emotional regulation (e.g., anger), use of sedatives, or support systems. In the broader Middle Eastern context, recent literature from Jordan, Egypt, and Iran has emphasized the need for Integrated psychosocial evaluation in oncology practice, showing how untreated distress can Exacerbate the overall disease burden (6)(7)(8)(9,10)

A recent study conducted across inpatient and outpatient oncology settings in Jordan reported that 23.4% of cancer patients exhibited depressive symptoms. In comparison, up to 37.6% showed signs of severe anxiety, particularly among inpatients and patients with advanced-stage disease. However, the antidepressant treatment was prescribed for only

15.5% of patients with depression or anxiety (11). These findings highlight A major unmet need in clinical care and reinforce the importance of early screening and targeted psychosocial support in cancer patients.

In Iraq, mental health services incorporation into oncology care remains substantially inadequate. Mental health professionals are scarce in most oncology centers, and psychological screening is not routinely performed during cancer diagnosis or follow-up. Cultural stigma surrounding mental illness may also contribute to the underreporting of emotional symptoms and poor help-seeking behavior. According to a 2023 WHO-EMRO report, less than 15% of patients in Iraq received psychological support, even though studies consistently demonstrate a high rate of undiagnosed mood disorders in this group of patients (12).

The present study aims to examine the psychosocial, clinical, and economic correlations of depression, anxiety, and stress among breast cancer patients in Al-Anbar city. Applying a multidimensional analytic approach, including multivariate linear and logistic regression, ROC analysis, and path modeling. This study explains how individual, emotional, and treatment-related factors interact to shape mental health outcomes. The findings are intended to guide more culturally sensitive and systemically integrated psychological interventions for cancer patients in Iraq and the region.

## **2-Materials and Methods**

### **2-1 Study design**

This is a cross-sectional observational study that was conducted between January and May 2025 in Al-Anbar Oncology Centre, Al-Anbar, Iraq.

### **2-2 Study population and sampling technique**

The study population consisted of all patients diagnosed with breast cancer who attended the Al-Anbar Oncology Centre in Al-Anbar, Iraq, between January 5th and May 30th, 2025.. Patients diagnosed with breast cancer at any stage and who provided informed consent to participate were included in the study.

### **2-3 Sample Size Calculation**

The sample size was calculated using the standard formula for cross-sectional studies, with the following parameters: a 95% confidence level, a 5% margin of error, and an expected prevalence of psychological distress of 50% to yield the largest possible sample size. Based on these assumptions, the minimum required sample size was estimated to be 384 participants. To enhance the statistical power and compensate for potential non-response or incomplete data, a larger sample was targeted. Consequently, a total of 500 breast cancer patients were enrolled in the final analysis, exceeding the minimum requirement.

### **2-4 Questionnaire tool and data extraction**

Patients' data were collected from medical records (demographics data, medication use history, and clinical profile). Cost data was obtained from the finance department at the center. Financial data included all available direct medical costs, such as treatment and physician visits. Moreover, patients were contacted to estimate the indirect cost associated with breast cancer therapy. A validated assessment tool, the Generalized Anxiety Disorder 7-item (GAD-7) and the Patient Health Questionnaire (PHQ-9) were used to assess anxiety and depression [Spitzer et al., 2006; Kroenke et al., 2001]. The patients were asked to determine the degree of applicability of each item (question) on a 4-point Likert scale. The participants' responses varied from 0 to 3, with 0 denoting "Not at all" and 3 denoting "Nearly every day." Nine elements comprise the PHQ-9 instrument. Items are scored on a scale of 0 to 3, resulting in a total score that ranges from 0 to 27. A total score of 0–4 indicates minimal depression, 5–9 mild depression, 10–14 moderate depression, 15–19 moderately severe depression, and 20–27 severe depression. Seven elements comprise the

GAD-7 instrument. Items are scored on a scale of 0 to 3, resulting in a total score that ranges from 0 to 21. Mild anxiety is indicated by a total score of 5–9, moderate anxiety by 10–14, and severe anxiety by 15–21.

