### 3 - Results

A total of 500 breast cancer patients were included in the final analysis. Descriptive statistics revealed a high prevalence of psychological distress within the sample, with elevated scores in depression, anxiety, and stress domains.

Spearman correlation analysis revealed strong positive associations between sleep difficulty and psychological outcomes: depression ( $r = 0.85$ ), anxiety ( $r = 0.77$ ), and stress ( $r = 0.85$ ), all statistically significant at  $p < 0.001$ . Use of sedatives was also significantly correlated with elevated distress scores ( $r > 0.90$  across models).

Kruskal-Wallis tests demonstrated statistically significant differences in mean ranks of depression, anxiety, and stress across cancer stages ( $p < 0.01$ ), with higher distress in patients with advanced-stage disease.

Multivariate linear regression identified the following as significant predictors of psychological distress:

- PHQ9\_Total:  $\beta = 0.42$ ,  $p < 0.001$
- Anger:  $\beta = 2.08$ ,  $p < 0.001$
- Cancer Stage:  $\beta = 0.92$ ,  $p = 0.0014$

Psychological support was not a significant predictor ( $p = 0.606$ ).

Binary logistic regression showed that PHQ9 and anger significantly predicted severe anxiety, with odds ratios of 1.32 and 1.27, respectively ( $p < 0.001$ ). Stage of disease also emerged as a significant factor in anxiety prediction.

Receiver Operating Characteristic (ROC) curve analysis yielded an Area Under the Curve (AUC) of 0.74 for stress in predicting severe anxiety, indicating a fair level of discriminative ability.

Finally, conceptual path analysis demonstrated that the relationship between stress and anxiety was primarily indirect, mediated through sleep disturbance and daily performance impairment. The direct path from stress to anxiety was negligible ( $r = -0.01$ ), suggesting a mediated mechanism of action.

**Table 1.** Descriptive Statistics of Study Variables

Variable	N	Minimum	Maximum	Mean	SD
Total Cost	500	80	34785	3721.69	4456.79
PHQ9_Total	500	1	27	17.99	6.11
GAD7_Total	500	1	21	12.79	3.81
Cancer Stage	500	0	4	2.52	1.09
Children	500	0	5	2.53	1.63
Metastatic	500	0	1	0.36	0.48
Stress Level	500	0	4	2.64	0.79

The descriptive characteristics of the study variables are presented in **Table 1**. Depression and anxiety scores were moderately high, while stress levels were also elevated. Treatment cost showed substantial variability across participants.

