Furthermore, Kruskal-Wallis analysis confirmed significant differences in mean ranks of depression, anxiety, and stress across cancer stages ( $H = 14.76$  to  $31.09$ ,  $p < 0.01$ ). These findings are supported by evidence from Iran and neighboring countries, where patients with stage III and IV breast cancer reported higher rates of emotional distress compared to the early stages of the disease (14). The increased psychological vulnerability in advanced stages underscores the need for stage-specific psychosocial interventions in cancer care protocols

Interestingly, total treatment cost showed a weak but statistically significant inverse correlation with psychological distress variables (e.g., PHQ-9\_Total:  $r = -0.11$ ,  $p = 0.017$ ). Although initially counterintuitive, this finding may reflect a perceived sense of security or access to higher-quality care among patients with greater financial capacity. Similar interpretations were reported in recent findings from Turkey, where patients with access to private sector services and higher financial resources exhibited lower levels of psychological distress despite elevated treatment costs, suggesting that financial ability may buffer emotional burden through enhanced control and perceived care quality (17).

As for psychological support, logistic regression models from this study suggested a protective effect ( $OR = 0.54$ ), though this was not statistically significant in the adjusted model ( $p = 0.606$ ). The lack of significance may be attributed to limited availability or underutilization of structured psychological services in the region, a challenge frequently reported in Iraq and across low-resource Middle Eastern settings. (18,19). Nonetheless, the direction of effect emphasizes the urgent need to integrate psychosocial support into routine oncology care.

Among all predictors examined, depression (PHQ9\_Total) and anger emerged as the strongest independent predictors of severe anxiety in both logistic and linear regression models ( $\beta = 0.42$  and  $2.08$ , respectively,  $p < 0.001$ ). These findings support prior research indicating that depressive symptomatology often precedes or co-occurs with anxiety in cancer patients, especially when emotional regulation is compromised (11)

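### Total Cost has no stated accrual window and no adjustment for time under care, and its sign reverses between Table 2 and Table 4, so the cost–distress association cannot be read as economic burden or financial capacity

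*Combined protocol and SAP*

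**What the plan says.** - **Objective (1-Introduction).** Economic correlates are one of three named domains: "The present study aims to examine the psychosocial, clinical, and economic correlations of depression, anxiety, and stress".
- **Population (2-2).** The study population is "all patients diagnosed with breast cancer who attended the Al-Anbar Oncology Centre in Al-Anbar, Iraq, between January 5th and May 30th, 2025". The inclusion rule adds only stage and consent: "Patients diagnosed with breast cancer at any stage and who provided informed consent to participate were included in the study". Neither sentence limits time since diagnosis or phase of treatment.
- **Cost (2-4).** Direct cost comes from the centre's finance department: "Financial data included all available direct medical costs, such as treatment and physician visits". Indirect cost was estimated by contacting patients. No start date, end date, recall period, currency or per-month scaling is given for either part. The contents of the analysed variable, Total Cost, are not defined.
- **Analysis (2-6, Tables 2 and 4).** Cost enters Spearman correlations and the linear models. The Table 4 covariates are sedative use, sleep variables, number of children and metastatic status. Time since diagnosis, treatment duration and treatment phase appear neither there nor in Table 1.
- **Results and interpretation.** Under Table 1 the text notes: "Treatment cost showed substantial variability across participants". The Discussion reports that "total treatment cost showed a weak but statistically significant inverse correlation with psychological distress variables" and offers patients' financial means as a possible explanation. Its opening paragraph lists economic burden among the factors significantly associated with distress.

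**The concern.** The design is cross-sectional, and depression, anxiety and stress each enter as one score per patient. A cost total without a defined window, taken in patients who may be anywhere from newly diagnosed to long-treated, is open to acting partly as a clock for time under care. If distress also changes along that course, cost and distress will correlate even when cost has no bearing on distress. The bias could run either way. If distress falls with time, it produces a spurious inverse correlation; if distress rises with time, it hides part of a real one.

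Total Cost is the only economic variable reported, so the whole economic strand depends on it. At stake is whether the Discussion may explain the inverse correlation by financial means, and whether economic burden belongs among the significant associations.

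**Working it through.** **Inputs.** From Table 1: n = 500; cost minimum 80, maximum 34,785, mean 3,721.69, SD 4,456.79; SD of PHQ-9 6.11, GAD-7 3.81, stress 0.79. From Table 2: cost correlations. From Table 4: cost coefficients with t and p. From the Discussion: r = -0.11, p = 0.017 for PHQ-9.

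**Step 1. Reproduce the stated correlation test.** t = r·√[(n-2)/(1-r²)] = -0.11·√(498/0.9879) = -2.47, two-sided p = 0.014. The stated 0.017 corresponds to r of about -0.107, so the two agree within rounding. r² = 0.0121, about 1.2% of rank variance.

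**Step 2. Reproduce the Table 4 cost tests.** With six listed predictors, df = 500 - 6 - 1 = 493. For PHQ-9, t = 2.209 gives p = 0.028, as stated. The stated p-values for GAD-7 (0.213) and stress (0.477) also reproduce.

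**Step 3. Set the two tables side by side.** The last two columns are B × 4,456.79, and that figure divided by the outcome SD.

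| Outcome | Table 2, Spearman r with cost | Table 4, B for cost | p for B | Change per SD of cost | Standardised |
|---|---|---|---|---|---|
| PHQ-9 | -0.11 | +7.5E-5 | 0.028 | +0.33 points | +0.055 |
| GAD-7 | -0.10 | +3.0E-5 | 0.213 | +0.13 points | +0.035 |
| Stress | -0.12 | +3.4E-6 | 0.477 | +0.015 points | +0.019 |

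The sign reverses for every outcome. For depression, both the negative correlation and the positive coefficient fall below 0.05.

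**Step 4. Sensitivity to time under care.** Let a be the correlation of cost with time and b the correlation of time with distress. The document gives neither, so both are assumptions. The partial correlation is

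(r - ab) / √[(1-a²)(1-b²)], with r = -0.11.

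| a | b = -0.3 | b = 0 | b = +0.2 |
|---|---|---|---|
| 0.3 | -0.022 | -0.115 | -0.182 |
| 0.5 | +0.048 | -0.127 | -0.247 |
| 0.7 | +0.147 | -0.154 | -0.357 |

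The two extremes are:
- a = 0.7, b = -0.3: (-0.11 + 0.21)/√(0.51 × 0.91) = 0.10/0.681 = +0.147.
- a = 0.7, b = +0.2: (-0.11 - 0.14)/√(0.51 × 0.96) = -0.25/0.700 = -0.357.

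Time would explain the correlation completely when ab = -0.11, that is b = -0.37, -0.22 or -0.16 for a = 0.3, 0.5 or 0.7.

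**Step 5. What the cost spread shows.** Maximum/minimum = 34,785/80 = 435, and SD/mean = 4,456.79/3,721.69 = 1.20. This spread fits unequal time under care. It fits differences in stage (0 to 4), metastatic status (36%) or type of treatment equally well, so it does not separate these explanations.

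**The case against.** The strongest reply is that accumulation over unequal time is nowhere stated. Section 2-4 gives no accumulation rule, and a common window such as the study period is compatible with its wording. This stands: the documented defect is the undefined window and the absence of any time variable. A reader might infer that costs were in fact summed from diagnosis. That is likely on the plain sense of the text, but the document does not say it.

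Three further points also stand.
- **Assumed correlations.** The range in step 4 has no documentary input and covers both directions. It shows that the sign is not identified; it does not show that the reported result is spurious.
- **Contents of Total Cost.** A reader might infer that direct and indirect cost were added together. The document describes two sources but never says they were summed, and elsewhere calls the variable treatment cost, which could mean direct cost only.
- **Limited reach.** The Discussion calls the correlation weak and words its explanation tentatively, and cost does not appear in the Clinical Implications or the Conclusion.

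The reply does not rescue the interpretation. The Discussion explains only the inverse correlation. It mentions neither the positive Table 4 coefficients nor time under care.

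**Conclusion.** The concern holds in limited form. Cost has no stated accrual window, the attenders are unrestricted by time since diagnosis, and no reported analysis standardises cost or adjusts it for time. The association accounts for about 1.2% of rank variance. Under the assumed correlations, adjustment for time could move it anywhere from about +0.15 to -0.36. Its sign already differs between Table 2 and Table 4. It therefore supports neither an economic-burden nor a financial-capacity reading.

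Two stronger conclusions are tempting and not supported:
- **That the economic objective cannot be answered.** The stated aim is correlational, and a crude correlation was estimated. What fails is the meaning attached to it.
- **That the sign reversal proves confounding by time.** Time is not among the Table 4 covariates. The reversal could come from the covariates that are there, or from moving from ranks to a linear scale on a widely spread variable. It shows only that the direction depends on the specification.

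The step 4 range rests entirely on the assumed values. The sign reversal and the missing window rest on the document alone.

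**What to change.** 1. Extract time since diagnosis from the medical records already used. Add it to the three Table 4 models and report the Table 2 cost correlations partialled for it.
2. State the accrual window, the currency and the contents of Total Cost. If it includes indirect cost, report the direct and indirect parts separately from the data already held. Patients need not be contacted again.
3. Where the finance records carry dates, repeat the cost analyses with direct cost over one common look-back, as a sensitivity analysis.
4. In any case, report in the Discussion that the cost association is negative in Table 2 and positive in Table 4 for all three outcomes.
5. If costs can be neither dated nor adjusted for time, remove the financial-capacity explanation from the Discussion paragraph on treatment cost, and remove economic burden from the associations listed in its opening paragraph.

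The cost is some re-extraction of dates and a rerun of the cost analyses, with no new recruitment. The downside is that cost over a common look-back will be noisier for recently diagnosed patients, whose records do not fill the window.

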## **2-6 Data Analysis**

Data was analyzed using IBM SPSS Statistics version 26. Descriptive statistics (mean, standard deviation, frequency, and percentage) were used to summarize demographic and clinical variables. The Kolmogorov-Smirnov test was applied to assess the normality of continuous variables, and due to non-normal distribution, non-parametric tests were used.

Bivariate analyses included Spearman's correlation coefficient to evaluate associations between psychological outcomes (depression, anxiety, stress) and continuous predictors such as sleep quality, cost, and number of children. The Kruskal-Wallis H test was employed to examine differences in distress levels across cancer stages.

Categorical associations were evaluated using Pearson's Chi-square test. Binary logistic regression analysis was conducted to identify predictors of severe anxiety. Additionally, multivariate linear regression models were constructed for each psychological outcome (PHQ-9, GAD-7, stress), and multicollinearity was assessed using the Variance Inflation Factor(VIF).

Receiver Operating Characteristic (ROC) curve analysis was used to assess the predictive accuracy of stress scores for severe anxiety, with Area Under the Curve (AUC) interpreted based on conventional thresholds. Conceptual path modeling was used to explore potential indirect relationships between stress and anxiety, mediated by sleep disturbance and impaired daily performance.

All tests were two-tailed, and a p-value of less than 0.05 was considered statistically significant.

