## 6-Conclusion

This study highlights the multifactorial nature of psychological distress among breast cancer patients in Al-Anbar, Iraq. Depression, anxiety, and stress were significantly linked to sleep disruption, sedative use, disease stage, and emotional dysregulation. Advanced cancer stage emerged as a key predictor of heightened anxiety and depression. These findings emphasize the need to integrate psychosocial assessment and targeted interventions into oncological care, particularly in low-resource settings, to mitigate psychological morbidity and improve quality of life in this population.

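### Stress is concluded on as a third outcome and called elevated with no described measure or reference value; separately, Sleep Satisfaction runs against its label in Tables 2 and 4

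*Combined protocol and SAP*

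**What the plan says.** Section 2-4 names two instruments: the "Generalized Anxiety Disorder 7-item (GAD-7) and the Patient Health Questionnaire (PHQ-9) were used to assess anxiety and depression". For both it gives the number of items, the response scale, the score range and severity bands. Its other sources are cost data, patient contact about indirect costs, and records: "Patients' data were collected from medical records (demographics data, medication use history, and clinical profile". It gives no instrument, item, range, direction or cut-off for stress, sleep difficulty, sleep satisfaction, sleep-related worry, anger, daily performance or psychological support.

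Stress nevertheless appears throughout:
- The Introduction gives the aim as the "psychosocial, clinical, and economic correlations of depression, anxiety, and stress among breast cancer patients".
- Section 2-6 says that "multivariate linear regression models were constructed for each psychological outcome (PHQ-9, GAD-7, stress" among them, and uses ROC analysis to "assess the predictive accuracy of stress scores for severe anxiety".
- Table 1 in Results reports "Stress Level 500 0 4 2.64 0.79" (N, minimum, maximum, mean, SD), and the text below it says "Depression and anxiety scores were moderately high, while stress levels were also elevated".
- Table 3 tests stress across cancer stages.
- The Conclusion says "Depression, anxiety, and stress were significantly linked to sleep disruption, sedative use, disease stage, and emotional dysregulation".

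Sleep Satisfaction appears in Table 2 and in the depression and anxiety models of Table 4. No text explains how it is scored.

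**The concern.** There are two separate problems.

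**Stress.** The mean PHQ-9 of 17.99 and mean GAD-7 of 12.79 can be placed in the bands of section 2-4 (15-19 and 10-14). The mean stress level of 2.64 cannot be placed anywhere. A reader cannot tell what was asked, what a 4 means, or what the level is elevated against, yet the Conclusion sets stress beside two validated scales.

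**Sleep Satisfaction.** Its sign contradicts its name. One of its coefficients is reported as significant (p = 0.045), so anyone reading Tables 2 and 4 at face value would take better sleep satisfaction to go with more depression, more anxiety and more sleep difficulty. The VIFs printed beside the sleep rows then raise the question whether those rows carry the right labels at all.

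**Working it through.** **1. The document's own figures.** The depression and anxiety models each list 6 predictors, so the residual df is 500 − 6 − 1 = 493. With p = 2·P(T > t):
- t = 2.01 gives 0.045, as printed.
- t = 1.886 gives 0.060, as printed.

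The printed p-values follow from the printed t statistics. The questions are direction, labels and VIFs.

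**2. Can the claim of elevated stress be checked?** The mean is 2.64/4 = 66% of the observed range. Its 95% CI is 2.64 ± 1.96 × 0.79/√500, or 2.57 to 2.71. The level is precisely estimated, but no threshold, norm or comparison group is given to set it against.

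**3. Direction of Sleep Satisfaction.** The inputs are the Table 2 row and N = 500. The interval is tanh(atanh r ± 1.96 × 1.06/√497), where 1.06/√497 = 0.0475.

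| With | r | 95% CI |
|---|---|---|
| Sleep Difficulty | +0.48 | 0.41 to 0.55 |
| PHQ-9 | +0.49 | 0.42 to 0.56 |
| GAD-7 | +0.62 | 0.56 to 0.67 |
| Stress | +0.55 | 0.48 to 0.61 |

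Every lower limit is above 0.40, so the sign is not sampling noise. The smallest eigenvalue of the Table 2 matrix is 0.074, so the signs are arithmetically possible. Both Table 4 coefficients agree with them (B = 0.364 and 0.539). The correlation with Total Cost (−0.09) also has the sign seen for the distress measures and Sleep Difficulty (−0.08 to −0.12). The variable behaves as if higher means worse, which its name denies.

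**4. VIFs in Table 4.** VIF = 1/(1 − R²), where R² comes from regressing that predictor on the others in its model. R² cannot be below the squared correlation with any one of them. The depression model contains both Sleep Satisfaction and Sleep Difficulty, with r = 0.48. Treating the Spearman value as Pearson:
- The floor is 1/(1 − 0.48²) = 1/0.7696 = 1.30. The table prints 1.021.
- Conversely, a VIF of 1.021 allows at most |r| = √(1 − 1/1.021) = 0.14.

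In the anxiety model the same label carries 4.866, to three decimals the value printed for Sleep Difficulty in the depression model. In R² terms, Sleep Satisfaction would go from 1 − 1/1.021 = 0.02 explained by the other predictors to 1 − 1/4.866 = 0.79 when Sleep Difficulty is replaced by Sleep-related Worry.

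**5. Text against table.** The sentence below Table 4 says that sedative use and sleep-related worry were significant predictors of stress, depression and anxiety. Table 4 has a Sleep-related Worry row for anxiety (B = 1.521) and for stress (B = 0.149). The depression model has none; its corresponding row is Sleep Difficulty (B = 4.52).

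**The case against.** The best defence is that this is a reporting gap. Table 1 gives Stress Level for all 500 patients, and Tables 2 and 4 report the sleep variables, so the data exist and a sound stress measure may have been used. That stands: a reader might infer that stress was never measured, and the documents do not support that. They show that it is undescribed.

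A reader might also infer that stress is not a separate construct, because its r = 0.85 with Sleep Difficulty means 0.85² = 72% shared rank variance, against 0.66² = 44% with PHQ-9 and 0.65² = 42% with GAD-7. Table 2 does not support this as a case against stress in particular. PHQ-9 has the same 0.85 with Sleep Difficulty, which also exceeds its 0.79 with GAD-7.

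It can be said, too, that no narrative passage interprets Sleep Satisfaction, and that the Discussion's link between stress and poor sleep is supported by Sleep Difficulty, which runs as labelled. That is correct. The contradiction lies in the tables, and the general finding on sleep is not reversed.

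Finally, the VIFs for sedative use, children, cost and metastatic status are identical in all three models although the listed predictors differ. Perhaps one larger model was fitted and only some rows printed, which could explain the missing worry row. But one common predictor set gives one VIF per variable, not 1.021 and 4.866, and the floor of 1.30 still applies. The doubt also weakens the Table 4 coefficients as support for the Table 2 signs, so the direction finding should rest mainly on Table 2.

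**Conclusion.** The point holds as two linked but separate defects.

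- One of three named outcomes has no described measure, and the statement that it is elevated has no reference in the documents.
- One sleep variable contradicts its label in all four relevant Table 2 correlations (0.48 to 0.62) and both Table 4 coefficients, one of them reported as significant. The Table 4 sleep rows are internally inconsistent, and one sentence reports a result for depression that the table does not contain.

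The sign and the mismatch between text and table are read directly from the document. The VIF floor assumes that the Pearson correlation is close to the Spearman one; to rescue 1.021 it would have to be 0.14 or less.

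The documents cannot show whether Sleep Satisfaction is reverse-coded, mislabelled or miscoded, or which Table 4 row is wrong. Nor do they show that stress is a single item: Table 1 gives only an observed range of 0 to 4. A reader might infer that stress must be dropped as an outcome and its linear model replaced, but that follows only if a single item without norms is confirmed.

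**What to change.** 1. Check the wording and coding of each sleep item against the questionnaire and dataset. Then reverse-score Sleep Satisfaction, or rename it to match its direction, in Tables 2 and 4. If only the coding is reversed, its correlations and coefficients change sign and the p-values stay the same.
2. Re-run the Table 4 models, list the full predictor set of each, and correct the sleep row labels and VIFs.
3. Correct the sentence on sleep-related worry and depression to match the re-run table.
4. Delete the statement that stress was elevated unless a stated threshold supports it.
5. In section 2-4, state the item or instrument, range and scoring direction actually used for stress and for each sleep, anger, daily-performance and support variable.
6. If stress proves to be a single item without norms, report it as exploratory, fit it with ordinal logistic regression on the same predictors, and limit the headline conclusion to PHQ-9 and GAD-7. If a sound measure with a cut-off was used, name it; stress can then stay.

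No new data are needed. The cost is a coding check, re-running existing models and text edits. The downside is a possibly narrower conclusion on stress.
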